8.2.2. Outcome Analysis

Descriptive statistics [number of participants, mean, standard error of the mean (SEM), standard deviation, median, interquartile limits, minimum and maximum] will be presented for continuous variables. Ratings for categorical variables will be presented as counts and percentages.

Baseline comparisons for demographic characteristics between control and active groups will be completed with the Chi-Square test, Fisher's exact (two-tail) tests, or analysis ofvariance (ANOVA), as appropriate.

A mixed model repeated measures analysis of covariance (ANCOVA) will be used to assess differences between study groups in continuous outcome variables. Initial ANCOVA models will contain terms for intervention, week, intervention by week interaction, and sex, with baseline measures (where applicable) as covariates. Models will be reduced using a backward selection method until only significant terms and/or intervention and baseline measures (where applicable) remain in the model. Pairwise comparisons between groups at each post-randomization visit will be conducted from the final ANCOVA model, with Dunnett's correction for multiple comparisons between each Medifast group vs. control. Assumptions of normality of residuals will be investigated for each response measurement. If the normality assumption is rejected at the I% level with the Shapiro-Wilk test (Shapiro 1965), then an analysis using ranks or other transformation will be performed.

Counts and percentages of participants who experience weight loss of :0:5% or :0:10% between baseline and each post-randomization visit will be presented. Differences between control and each active group participants with weight loss :0:5% or :0:10% will be assessed using a generalized linear model with a logit link and binomial distribution specified. Initial repeated measures models will contain terms for intervention, week, intervention by week interaction, and sex. Models will be reduced using a backward selection method until only significant terms or intervention remains **in** the model. Pairwise comparisons at each post-randomization visit will be conducted using Dunnett's correction for multiple comparisons between each Medifast group vs. control.

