### **3.0. SIZE OF TRIAL POPULATION**

A standard deviation of 15.0 lb for change in body weight over 16 weeks was derived from the largest variability observed in a previous study by Davis et al. (2010) that compared weight loss over 16 weeks on the Medifast 5 & 1 Plan® (-29.8 ± 13.0 lb) vs. a food-based isocaloric control diet (-14.3 ± 15.0 lb). Using this estimate of expected variability and accounting for a more conservative mean difference in weight loss between groups over a similar timeframe, an evaluable sample of 55 participants in each group (165 total) will provide 80% power to detect a difference of 9.0 pounds (an effect size  $d$  of 0.60). This assumes a nominal  $\alpha = 0.025$  (two-sided) accounting for two primary comparisons, each Medifast group compared to the control group, in order to maintain an overall type I error of  $\alpha = 0.05$ . To account for possible attrition, a total sample of 198 participants will be randomized.

Subjects will be randomized to one of three groups (1:1:1 ratio) stratified by sex to ensure each group is allocated a maximum of 25% male participants. Additionally, the total study sample will be limited to  $\leq 10\%$  of participants with a BMI between  $\geq 27.0$  and  $< 30.0$  kg/m^2, but randomization will not be stratified by BMI.

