### 9.0. STATISTICAL METHODS

Descriptive statistics (number of subjects, mean, SEM, median, interquartile limits, minimum and maximum) will be presented for quantitative variables. Ratings for categorical variables will be presented as counts and percentages. All tests of significance, unless otherwise stated, will be performed at alpha=0.05, two-sided.

Baseline comparisons for demographic characteristics between control and intervention groups will be completed with the Chi-square test, Fisher’s exact (two-tail) test, or analysis of variance (ANOVA), as appropriate.

Analysis of covariance (ANCOVA) will be used to assess differences among intervention groups in the primary and continuous secondary outcome variables at each post-randomization visit. The ANCOVA model will contain a term for intervention, with sex and baseline measures as covariates. Least squares mean values and corresponding SEM will be derived from the final ANCOVA model for each intervention group.

Counts and percentages of subjects who experience weight loss of  $\geq 5\%$  and  $\geq 10\%$  between baseline (Visit 2) and each post-randomization visit (visits 3, 4, 5, 6, and 7) will be presented. Differences among intervention groups in subjects with weight loss of  $\geq 5\%$  and  $\geq 10\%$  will be assessed using a generalized linear model with a logit link and binomial distribution specified. The model will contain a term for intervention, with sex as a covariate.

Differences among intervention groups in individual Satisfaction and Health/Well-being questionnaire scores will be assessed using a generalized linear model with a cumulative logit link and multinomial distribution specified. The model will contain a term for intervention, with sex and absolute change in weight as covariates.

For the analyses of body weight, body composition parameters, and body circumference parameters, each active group will be compared to the control group using a step-down Dunnett adjustment for multiple comparisons when a significant treatment effect is observed. Meanwhile,

no adjustments will be done on control vs. active comparisons on the remaining outcome variables.

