Descriptive statistics will be provided for the Program Questionnaire outcomes. Also, linear association between change (absolute) in body weight from baseline (Visit 2; week 0) to end of study (Visit 7; week 16) and average meal replacements [averaged across Visits 4 to 7 (weeks 4-16)] will be obtained (spearman's rank-order correlation) for the MEDD and TSFL groups. Additionally, for the TSFL group, linear association between change (absolute) in body weight from baseline (Visit 2; week 0) to end of study (Visit 7; week 16) and number of coaching contacts will be obtained (spearman's rank-order correlation). Lastly, for the MEDD group, association between whether subjects made discretionary Nutrition Support contact(s) or not and weight loss of  $\geq 5\%$  will be assessed using a Fisher's exact test.

Assumption of normality of residuals will be investigated for each outcome variable at the 5% level of significance with the Shapiro-Wilk test (Shapiro 1965). If the normality assumption is not satisfied, then an analysis based on ranks will be performed.

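### SAP 9.0 makes the body-weight comparisons wait on an overall test that step-down Dunnett does not need, and a normality test chooses the scale of the primary p-value; both are cheap to remove

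*SAP*

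**What the plan says.** **Gate.** For body weight, body composition and circumferences, SAP 9.0 compares each active arm with control "using a step-down Dunnett adjustment for multiple comparisons when a significant treatment effect is observed". It gives no level for that overall test. The general rule in the same section is "All tests of significance, unless otherwise stated, will be performed at alpha=0.05, two-sided", and the shell for Table 3 has a column for an overall intervention p-value. Protocol 8.2.2 plans pairwise comparisons "with Dunnett's correction for multiple comparisons between each Medifast group vs. control" and sets no overall-test condition. The sample size in SAP 3.0 (the same as Protocol 8.1) says "an evaluable sample of 55 participants in each group (165 total) will provide 80% power to detect a difference of 9.0 pounds". It rests on two comparisons at two-sided 0.025 and makes no allowance for a gate.

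**Normality rule.** SAP 9.0: "Assumption of normality of residuals will be investigated for each outcome variable at the 5% level of significance with the Shapiro-Wilk test". And: "If the normality assumption is not satisfied, then an analysis based on ranks will be performed". Table 3, the primary table, carries an (r) marker for rank-based p-values. Protocol 8.2.2 already had such a rule at 1% (the digit is garbled in the extracted text), after which "then an analysis using ranks or other transformation will be performed". Under SAP 8.1 the primary variable is both absolute and percent weight change.

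**Change list.** SAP 14.0 records changes to populations, primary variable, secondary variables, missing data and outliers. It records none to the statistical methods of Protocol 8.2.2.

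**The concern.** Step-down Dunnett is a complete familywise procedure for two arms against one control. An overall test placed in front of it adds no protection and can block a comparison that the procedure would declare. The trial could then show TSFL beating control at the adjusted level and be unable to say so, because a 2-df test missed 5%. This is most likely when MEDD falls between control and TSFL.

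The normality rule raises a different question. The trial was sized on a mean difference in pounds. If the rule fires, the primary p-value tests ranks instead. Because the rule is applied to each outcome variable, absolute and percent change can end on different methods. The SAP also does not say how the rule works across multiply imputed ITT datasets.

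**Working it through.** **1. The plan's own figure.** Inputs (SAP 3.0): difference 9.0 lb, SD 15.0 lb, two-sided 0.025, 55 per arm.
- d = 9.0/15.0 = 0.60.
- Noncentrality = 0.60 × √(55/2) = 3.15.
- The two-sample t-test gives n = 54.08, rounded up to 55, and power 80.7% at 55. The stated figure reproduces, with no gate in it.

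**2. Why the gate can block a Dunnett-significant result.** Critical values at 55 per arm (162 df): Dunnett 2.232; overall F (2, 162 df) at 5% 3.052. Let the observed MEDD difference be a fraction *a* of the observed TSFL difference, and *t* the TSFL statistic. With three equal groups,

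F = (2/3)(1 − a + a²) t².

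- At a = 0 or 1, F > 3.052 needs t > √(1.5 × 3.052) = 2.14. That is below 2.232, so nothing is blocked.
- At a = 0.5, F = t²/2, so it needs t > √(2 × 3.052) = 2.47. The SE of a difference is 15.0 × √(2/55) = 2.86 lb. A TSFL difference between 2.232 × 2.86 = 6.4 lb and 2.47 × 2.86 = 7.1 lb therefore passes Dunnett and is withheld.
- Blocking a TSFL result that passes 2.232 needs 1 − a + a² < 1.5 × 3.052/2.232² = 0.919, so *a* lies between about 0.09 and 0.91.

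**3. Size of the loss.** Simulation, 1,000,000 trials per setting: 55 per arm, TSFL d = 0.60, normal errors, no covariate gain, gate at 5%.

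| MEDD d | TSFL power, no gate | with gate | loss (points) |
|---|---|---|---|
| 0 | 82.0% | 81.1% | 0.9 |
| 0.15 | 81.9% | 79.4% | 2.5 |
| 0.30 | 82.4% | 78.9% | about 3.6 before rounding |
| 0.45 | 83.8% | 81.2% | 2.6 |
| 0.60 | 85.9% | 85.0% | 0.9 |

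Familywise error under the global null is 5.0% without the gate and 3.7% with it. On a finer grid, gated power is below 80% for MEDD d of about 0.15 to 0.35.

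**4. Sensitivity of the shortfall.**
- Covariates: if sex and baseline explain 3% of variance, the effective d is 0.60/√0.97 = 0.609 and gated power at MEDD d = 0.30 is 80.2%. At 5% explained (0.60/√0.95 = 0.616) it is 81.1%.
- All 66 per arm observed: 86.5 to 91.3% across the same MEDD effects.
- Pooled SD from the cited study: √((13.0² + 15.0²)/2) = 14.04 lb, so d = 0.64. Gated power is 84.5 to 89.7%.
- The cited study's own difference, 29.8 − 14.3 = 15.5 lb: loss under 0.1 point.

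**5. Normality switch.** The documents give no residual shape, so the shapes are assumed. Simulated firing rates at n = 165 (6,000 samples per shape):

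| Residuals | fires at 5% | fires at 1% |
|---|---|---|
| normal | 5% | 1% |
| gamma, skew 0.3 | 28% | 12% |
| gamma, skew 0.5 | 63% | 40% |

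The next figures assume a baseline weight of 215 lb (SD 25 to 35), TSFL 9.0 lb and MEDD 4.5 lb better than control, and no gate (2,500 trials per setting). For the three shapes in turn, absolute and percent change land on different methods at the 5% level in 4–11%, 9–16% and 11–17% of trials. The TSFL verdict differs from always using ANCOVA in 0.2–0.7%, 1.2–1.8% and 2.8–3.9%. The 5% and 1% rules reach different verdicts in 0.1–1.2%. Ungated familywise error is 4.8–5.0% with ANCOVA throughout and 5.1% with the switch.

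**The case against.** The strongest reply is that the plan is sized for 9.0 lb in each Medifast arm. On that assumption gated power is about 85%, above the planned 80.7%. A figure under 80% needs an intermediate MEDD effect that the documents do not state, and also no benefit from covariates that the SAP model contains. This stands, and it limits the claim. A reader might infer that the gate leaves the trial underpowered; the documents do not support that.

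A reader might also infer that the SAP rule is weaker than the protocol's. That is not shown. Protocol 8.2.2 specifies a repeated-measures model with backward selection, which was not simulated. Even against single-step Dunnett at one visit, the gated step-down rule is not uniformly worse. For MEDD at d = 0.30 its power is 33.6% against 25.8%, and with both arms at d = 0.60 both comparisons succeed in 79.4% against 71.4%. The step-down element supplies that gain and the gate trims it, so this does not defend the gate.

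On normality, the switch was already prespecified in the protocol. The SAP narrowed the fallback to ranks and changed the level; it did not introduce the idea. Table 3 still reports raw and least squares mean changes, and the (r) marker is attached only to p-values. That stands too. What remains is that the hypothesis behind the primary p-value is not fixed until the residuals are seen.

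**Conclusion.** The concern holds, at modest size. The gate gives no error control that step-down Dunnett lacks. It makes the procedure conservative (3.7% against 5.0%) and costs 0.9 to 3.6 points of TSFL power at d = 0.60 with 55 per arm. A shortfall below 80% (minimum about 78.9%) is confined to an assumed MEDD effect of d about 0.15 to 0.35 with no covariate gain. If sex and baseline explain 3 to 5% of variance, the figure at MEDD d = 0.30 is about 80 to 81%. All of this takes the gate level as 5%, which is inferred.

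The normality switch is secondary. It leaves open which quantity the primary p-value tests and whether the two primary measures share a method. It would be wrong to read it as inflating type I error or as often changing the conclusion: under the assumed shapes neither occurs. The incomplete change list is a documentation gap. Overall priority is minor to moderate.

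**What to change.** (a) In SAP 9.0, delete the condition on a significant treatment effect and apply step-down Dunnett directly.

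(b) Name ANCOVA on the untransformed scale as the primary analysis of absolute and percent weight change whatever the Shapiro-Wilk result, in every population and every imputed dataset. Report the rank analysis as a sensitivity analysis.

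(c) As housekeeping, list in SAP 14.0, with reasons, every method change from Protocol 8.2.2 that remains:
- repeated-measures models with backward selection replaced by per-visit ANCOVA, and by a responder model with intervention and sex only;
- Dunnett replaced by step-down Dunnett for weight, composition and circumference outcomes;
- no adjustment for the remaining outcomes;
- weight change added as a covariate in the satisfaction model;
- the revised normality rule.

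The cost is SAP wording and one sensitivity table, with no new data and no change in sample size.

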8.1. Sample Size

A standard deviation of 15.0 lb for change in body weight over 16 weeks was derived from the largest variability observed in a previous study by Davis et al. (2010) that compared weight loss over 16 weeks on the Mcdifast 5 & I Plan@ (-29.8 \pm 13.0 lb) vs. a food-based isocaloric control diet (-14.3 \pm 15.0 lb). Using this estimate of expected variability and accounting for a more conservative mean difference in weight loss between groups over a similar timefi'ame, an evaluable sample of 55 participants in each group (165 total) will provide 80% power to detect a difference of 9.0 pounds (an effect sized of 0.60). This assumes a nominal a = 0.025 (two-sided) accounting for two primary comparisons, each Medifast group compared to the control group, in order to maintain an overall type I error of a = 0.05. To account for possible attrition, a total sample of 198 participants (n = 66 *I* group) will be randomized.

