
Table 4.10  
Secondary Outcome Variable: Weight Loss Program Adherence Descriptive Statistics and P-values

Parameter		TSFL	MEDD
Meal Replacement^	Mean (SEM)	Mean (SEM)	Mean (SEM)
	Median	Median	Median
	Q1, Q3	Q1, Q3	Q1, Q3
	Min, Max	Min, Max	Min, Max
	Corr (p-value)+	0.xxx (x.xxx)	0.xxx (x.xxx)
Nutrition Support Contact	Mean (SEM)	Mean (SEM)	Mean (SEM)
	Median	Median	Median
	Q1, Q3	Q1, Q3	Q1, Q3
	Min, Max	Min, Max	Min, Max
Coaching Contact	Mean (SEM)	Mean (SEM)	
	Median	Median	
	Q1, Q3	Q1, Q3	
	Min, Max	Min, Max	
	Corr (p-value)+	0.xxx (x.xxx)	

^average meal replacement (per day) across the 16-weeks of the study

+spearman's rank-order correlation between the corresponding parameter and absolute change in body weight from baseline (Visit 2; week 0) to end of study (Visit 7; week 16)

Table 4.11  
Secondary Outcome Variable: Nutrition Support Contact P-values

Group	Parameter	Initial & Discretionary NS contact*		Initial NS contact or None**	p-value^
MEDD	% weight loss >= 5%	N (%)	N (%)	N (%)	x.xxx
TSFL	% weight loss >= 5%	N (%)	N (%)	N (%)	x.xxx

^p-values shown are generated from Fisher's exact test

\*at least two NS contacts for MEDD or at least one NS contact for TSFL

\*\*at most one NS contact for MEDD or none for TSFL

Table 5  
Summary of Subjects with at Least One Intervention-emergent Adverse Events

	Control	TSFL	MEDD	Intervention p-value*
Any Adverse Event	N (%)	N (%)	N (%)	x.xxx
Serious	N (%)	N (%)	N (%)	x.xxx
Severe	N (%)	N (%)	N (%)	x.xxx
Related to Study Treatment*	N (%)	N (%)	N (%)	x.xxx

\*p-values shown are generated from Chi-Square or Fisher's exact test, as appropriate

\* Probably or Definitely Related to Study Treatment.

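### The adherence–weight correlations in SAP Table 4.10 use absolute weight change without adjusting for baseline weight or sex, so they can be confounded by body size and can lose power

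*SAP*

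**What the plan says.** Protocol section 4 makes the relation between weight change and self-reported adherence part of the secondary objectives. SAP 9.0 carries this out with a "linear association between change (absolute) in body weight from baseline (Visit 2; week 0) to end of study (Visit 7; week 16" and two adherence measures: meal replacements averaged over Visits 4 to 7 (TSFL and MEDD), and number of coaching contacts (TSFL only). The method is Spearman's correlation and no covariates are named. The Table 4.10 footnote repeats this as a "rank-order correlation between the corresponding parameter and absolute change in body weight from baseline", and the shell reports a p-value for each correlation. No adjusted or percent-change version is planned.

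For the continuous outcomes, body weight included, SAP 9.0 states: "The ANCOVA model will contain a term for intervention, with sex and baseline measures as covariates". The Table 3 footnote confirms the adjustment for both absolute and percent weight change.

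For the ≥5% and ≥10% responder analyses SAP 9.0 states: "The model will contain a term for intervention, with sex as a covariate". Baseline weight is absent there, as it is from the responder model in protocol section 8.2.2.

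**The concern.** Randomisation protects the between-group ANCOVAs, and those are adjusted. It gives no protection to a correlation within one arm between what participants report doing and what they lose, and that comparison is unadjusted. The outcome is absolute change. Eligible BMI runs from 27.0 to 42.0 kg/m², a ratio of 42/27 = 1.56, and up to 25% of participants may be men, so expected absolute loss can differ with body size and sex.

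Two things could follow. If adherence also varies with baseline weight or sex, the correlation can show an association that is not due to adherence, or hide one that is. If adherence does not vary with them, body size is noise in the outcome and lowers power. Either could change what the trial reports on a stated secondary objective.

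**Working it through.** **Inputs from the documents.** The planned evaluable number is 55 per group of 66 randomised (SAP 3.0; protocol 8.1). General tests "will be performed at alpha=0.05, two-sided". The sample size rests on "A standard deviation of 15.0 lb for change in body weight over 16 weeks" and "80% power to detect a difference of 9.0 pounds". The cited earlier study gives −29.8 ± 13.0 lb on the 5 & 1 Plan and −14.3 ± 15.0 lb on its control diet.

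**The plan's own figure.** With d = 9/15 = 0.60 and two-sided α = 0.025, the normal formula gives n = 2(2.241 + 0.842)²/0.60² = 52.8, so 53 per group. The exact t-test has 79.9% power at 54 and 80.7% at 55, so 55 reproduces, and 165/(1 − 1/6) = 198. None of this depends on the present point. Neither document states power for the correlations or the responder models.

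**How strongly might baseline weight relate to absolute change?** The documents do not say. If everyone loses the same expected percentage, r(baseline, change) = mean loss × CV of baseline weight / SD of change. With an assumed CV of 30/215 = 0.14:
- at the 5 & 1 Plan figures, 29.8 × 0.14/13.0 = 0.32;
- at the control-diet figures, 14.3 × 0.14/15.0 = 0.13.

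The range 0.2 to 0.6 is used below. Its top lies well above what proportional loss alone would produce.

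**Confounding with no true adherence effect.** The induced Pearson correlation is r(baseline, change) × r(baseline, adherence). On the Spearman scale ρ = (6/π) arcsin(product/2). The test uses Fisher's z with variance 1.06/(n − 3). Worked extreme: 0.6 × 0.3 = 0.18; ρ = 0.172; z = 0.174/√(1.06/52) = 1.22; two-sided rejection 23%.

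Rejection at nominal 5%, n = 55:

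| r(baseline, change) | r(baseline, adherence) = 0 | 0.1 | 0.2 | 0.3 |
|---|---|---|---|---|
| 0.2 | 5.0% | 5.2% | 5.8% | 6.9% |
| 0.4 | 5.0% | 5.8% | 8.4% | 12.7% |
| 0.6 | 5.0% | 6.9% | 12.7% | 23.0% |

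At n = 66 the extreme cell is 26.8%. A separate simulation (8,000 data sets per setting, n = 55) gave 9.6% at (0.3, 0.3), 17.8% at (0.5, 0.3) and 24.0% at (0.6, 0.3) for the plain test. The partial Spearman test stayed at 4.9% to 5.1%.

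**Power with no confounding.** Assume a partial correlation of 0.35 and adherence unrelated to baseline weight. The unadjusted correlation is 0.35 × √(1 − r²), where r = r(baseline, change). The adjusted test keeps 0.35, with variance 1.06/(n − 4) for one covariate.

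| r(baseline, change) | unadjusted correlation | power, unadjusted | power, adjusted |
|---|---|---|---|
| 0.2 | 0.343 | 71% | 72% |
| 0.4 | 0.321 | 64% | 72% |
| 0.6 | 0.280 | 52% | 72% |

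Adding sex as a second covariate that explains nothing further changes 51 to 50 in the variance: 0.3654/√(1.06/50) = 2.51, power 71%. The extra covariate costs under one point, which roughly cancels the gain in the first row.

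**Responder model (≥5% loss).** Simulation with 66 per arm, assumed mean weight 215 lb, control loss 5% and active loss 9 lb greater; 1,500 runs per setting, Monte Carlo error about 1 point. Power without and with baseline weight was 77% and 76% if r(baseline, percent loss) = 0, 76% and 78% at 0.2, and 77% and 81% at 0.4. Under no group difference, rejection was 4% to 6% with or without the covariate. A second simulation (55 per arm, difference 0.6 SD) gave 69.3% to 69.4% at r = 0.1 and 69.5% to 73.9% at r = 0.4. The gain is therefore about 0 to 5 points.

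**The case against.** The strongest reply is that confounding is assumed. Every TSFL participant is assigned five replacements a day and every MEDD participant four. Orders are fixed at 140 and 112 per four weeks, which is 5 × 28 and 4 × 28. Snacks and Flavors of Home meals are left out of the count, and all TSFL participants share one coaching schedule. A reader might infer from the missing covariates that adherence effects are in fact mixed with body size. The documents do not support that, because they give no link between adherence and baseline weight, and with no link the null rejection rate stays at 5%. This part of the objection stands. It does not remove the risk: the analysed variable is reported intake, Program Questionnaire question 6 accepts 0 to more than 6, and the SAP codes the top answer as 7, so departures from the assigned number are expected.

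A reader might also take these correlations to be the trial's only tests of adherence against weight loss. They are not. SAP 9.0 also plans a Fisher's exact test of discretionary Nutrition Support contact against ≥5% loss in MEDD, and the Table 4.11 shell shows it for TSFL too. That outcome is already scaled to baseline weight.

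The adherence argument cannot be extended to the responder model, which compares randomised groups, contains no adherence term and follows the protocol. Adding a prognostic covariate there also changes the odds ratio to one conditional on baseline weight and raises its standard error (0.377 to 0.405 at r = 0.4), even though power rises.

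Finally, the protocol says only that these relationships will be examined, and adjusting for weight and sex would leave motivation and other confounders in place. That limits how much the result can bear, but it is no reason to leave out two measured variables that the SAP already uses elsewhere.

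**Conclusion.** The point holds for the Table 4.10 correlations as a risk of confounding and a possible loss of power. Null rejection runs from 5% with no adherence–body-size link to about 23% at n = 55, and the upper figure needs both assumed correlations at the top of their range. Where baseline weight correlates 0.2 to 0.4 with change, the range is 5% to 13%. The power loss without confounding is about 1 to 20 points at partial r = 0.35 and is negligible when baseline weight explains little of the change. All correlations with baseline weight are assumptions. The effect of sex was not modelled separately, and n = 55 stands for participants with a week-16 weight.

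For the responder models the omission is minor: about 0 to 5 points of power and no type I inflation. The primary comparison of body weight already adjusts for sex and baseline and is unaffected.

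**What to change.** In SAP 9.0 and the Table 4.10 footnote, pre-specify partial Spearman correlations of week-16 absolute weight change with average meal replacements (TSFL, MEDD) and with coaching contacts (TSFL), adjusted for baseline weight and sex. Describe them as associations, since adherence is not randomised.

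Optionally, name baseline weight as a covariate in the ≥5% and ≥10% logit models, or as a sensitivity analysis, and amend the Table 4.2 footnote. State that the odds ratio is then conditional on baseline weight. State in advance how visits with very few responders will be handled, for example by a penalised likelihood, so that the covariate is not dropped ad hoc.

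The data are already collected. The cost is a few lines of SAP text and small changes to the correlation and logit code. Making the change before analysis avoids a post hoc choice.

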 - Adherence will be calculated based on self-reported TSFL/MEDD meal replacement product consumption, participation at assigned coaching sessions (TSFL only), utilization of Nutrition Support (TSFL/MEDD), and a single question VAS rating adherence to their assigned weight loss program (all groups).
- Participant satisfaction and health/well-being assessed via the Satisfaction and Health/Well-being Questionnaire at Visit 7 (week 16).
- Absolute change in hs-CRP from baseline (Visit 2; week 0) to Visit 7 (week 16).

Jason Pharmaceuticals, Inc. BI0-1607 (MED 019) 21 June 2016; Version 1.7 1012 CT 1022 CT

8. Data Analysis and Statistical Methods

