  - IWQOL-Lite Questionnaire (Kolotkin RL, et al. 2001) is a 31-question self report instrument to assess obesity specific quality of life and consists of five domains: Physical Function (11 questions), Self-Esteem (7 questions), Sexual Life (4 questions), Public Distress (5 questions), and Work (4 questions). The domain scores will be the sum of the ratings on questions that correspond to the specific domain. A total score (all 31 questions) will also be presented.
- Participant satisfaction and health/well-being assessed using the Satisfaction and Health/Well-Being Questionnaire at Visit 7 (week 16). Responses will be coded as follows: “1” and “2” = “Disagree”, “3”= “Neither agree nor disagree”, and “4” and “5”= Agree.
- Absolute change in hs-CRP from baseline (Visit 2; week 0) to Visit 7 (week 16)
- Weight loss program adherence assessed at Visits 4, 5, 6, and 7 (weeks 4, 8, 12, and 16) based on the Program Questionnaire. Adherence will be calculated based on self-reported TSFL/MEDD meal replacement product consumption (active groups only) and a single question VAS rating adherence to their assigned weight loss program (all groups). For the self-reported TSFL/MEDD meal replacement product consumption, if the subject encircled “>6”, it will be coded as “7”. Also, questions (1,2) and (4,5) of the Program Questionnaire will be scored as:

		Leisure Time Activity				
		Very Light	Light	Moderate	Active	Very Active
Working/School Activity	Very Light	1.4	1.5	1.6	1.7	1.9
	Light	1.5	1.6	1.7	1.8	2.0
	Moderate	1.6	1.7	1.8	1.9	2.2
	Heavy	1.7	1.8	1.9	2.1	2.3

- Participation at assigned coaching sessions as a measure of adherence for the TSFL group.
- Utilization of Nutrition Support for the TSFL and MEDD group.

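### The one inferential Nutrition Support analysis cuts both contact and weight change to yes/no, while the same SAP paragraph keeps weight change on its full scale for coaching and meal replacements

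*SAP*

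**What the plan says.** SAP 8.2 lists "Utilization of Nutrition Support for the TSFL and MEDD group" among the secondary outcomes, and Protocol 7.2 counts it as a component of adherence.

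SAP 9.0 handles three support or adherence measures in one paragraph:

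- **Meal replacements (MEDD and TSFL):** Spearman correlation of average intake with absolute weight change to week 16.
- **Coaching (TSFL):** the same method, where the association of weight change with "number of coaching contacts will be obtained (spearman's rank-order correlation").
- **Nutrition Support (MEDD):** contact yes/no against at least 5% loss yes/no. The "association between whether subjects made discretionary Nutrition Support contact(s) or not and weight loss of" at least 5% "will be assessed using a Fisher's exact test".

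The table shells in SAP 17.0 add detail. Table 4.10 summarises the Nutrition Support contact count in both active arms. It gives that row no correlation line, although the meal-replacement and coaching rows have one. Table 4.11 gives a Fisher p-value for MEDD and also for TSFL. Its exposed group is "at least two NS contacts for MEDD or at least one NS contact for TSFL" and its reference group is "at most one NS contact for MEDD or none for TSFL".

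**The concern.** Weight change is continuous and the number of contacts is a count, so the planned test discards information in both variables. Fisher's test is also conservative in small samples. Nutrition Support is the only personal support described for MEDD after randomisation. Its association with weight loss would be judged by a less sensitive method, on a different outcome, than the TSFL coaching result reported beside it. A non-significant Fisher result is then hard to interpret, and the two support results cannot be compared.

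The text and the shell also disagree. Section 9.0 plans the test in MEDD only, while Table 4.11 has a p-value row for TSFL. Their definitions can differ within MEDD too. Protocol 6.4.1 foresees that the initial call may not take place. A participant who missed it and later phoned once has made a discretionary contact under section 9.0, but falls in the shell's reference group with one contact.

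**Working it through.** **1. The plan's own figure.** SAP 3.0 gives SD 15.0 lb, difference 9.0 lb, two-sided alpha 0.025 and 80% power.

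- n per group = 2(z₀.₉₈₇₅ + z₀.₈₀)² × SD²/difference² = 2(2.241 + 0.842)² × 225/81 = 52.8, so 53.
- At 55 per group the noncentral t distribution gives 80.7%, so the stated 55 and 80% hold.
- 198/3 = 66 are randomised per arm.

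This power belongs to the randomised comparison with control. No power is stated for the Nutrition Support test.

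**2. Inputs for the Nutrition Support test.**

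- From the plan: 55 evaluable per arm, SD 15 lb, two-sided alpha 0.05 (SAP 9.0).
- Assumed mean MEDD loss: 14.3-23.3 lb. The lower end is the food-based control arm of the earlier study cited in SAP 3.0; the upper end is 14.3 + 9.0.
- Assumed baseline weight: 200-225 lb, so the 5% cut is 10 to 11.25 lb.
- Assumed share with discretionary contact: 25% or 50%.
- Assumed gap in weight loss between contact groups: 9, 6 or 3 lb.
- Assumed visit for the 5% outcome: week 16, since neither section 9.0 nor the Table 4.11 shell names one.

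**3. One case by hand.** Take share 25% (14 vs 41 participants), mean 14.3 lb, gap 9 lb and a fixed cut at 10 lb.

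- Group means: 14.3 + 0.75 × 9 = 21.05 lb and 14.3 − 0.25 × 9 = 12.05 lb.
- Responder rates: Φ((21.05 − 10)/15) = 0.77 and Φ((12.05 − 10)/15) = 0.55.
- t-test noncentrality: 9/(15√(1/14 + 1/41)) = 1.94, giving power 47.7%.
- Exact Fisher power for 0.77 vs 0.55: 21.8%.
- Difference: about 26 points. With a mean of 20 lb the responder rates are 0.87 and 0.70, and power is 47.7% vs 17.4%, about 30 points.

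**4. Simulation over the assumed ranges.** Both tests use the same yes/no contact groups, so only the outcome differs.

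| Assumed gap | Gain of Wilcoxon over Fisher |
|---|---|
| 9 lb | about 20-35 points |
| 6 lb | about 10-17 points |
| 3 lb | about 3-8 points |

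At 9 lb, Fisher has about 11-36% power and Wilcoxon about 45-58%. With no association, Fisher rejects in about 3.5% of samples, against a nominal 5%. A rerun agreed with these figures to within about two points.

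**5. Keeping the count as well.** This step models contacts as negative binomial or Poisson with an assumed latent correlation with weight loss, n = 55-66, contact share 25-50% and 50-80% responders. Spearman on the full scales gains over Fisher 0-3 points at correlation 0, 3-8 at 0.1, 9-18 at 0.2, 16-36 at 0.3 and 24-50 at 0.4. For example, with n = 55, half making contact, 65% responders and correlation 0.3, power is 48.6% vs 23.2%.

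**The case against.** **The size is not fixed by the plan.** A reader might infer that the planned test simply forfeits 20-35 points. The documents do not support that. The 9 lb gap is borrowed from the randomised program-versus-control difference, and nothing suggests that optional calls separate participants by as much. At smaller gaps the gain shrinks quickly. This part of the objection stands, so every figure must carry its condition.

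**The better test is still weak.** Wilcoxon reaches only about 45-58% at 9 lb, and 25-27% if just 10% of the arm makes contact. This stands too. The change improves an exploratory analysis and does not make it well powered.

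**The 5% cut is not arbitrary.** At least 5% loss is a pre-specified secondary outcome, and separating discretionary contact from the scheduled call is sensible. That justifies reporting the counts. It does not explain why the association is tested on them. Nor can the cut be called badly placed in general: at a mean loss of 14.3 lb about 58-61% would be responders, near the middle, and only the 23.3 lb end gives about 80%.

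**Other readings that go too far.** Fisher's test is not the only Nutrition Support analysis, since Table 4.10 describes the count. Nor is it confined to one arm in the shell. The programs do not differ mainly in support either: Protocol 6.4.1 gives them different energy levels and different numbers of meal replacements. Because contact is self-selected after randomisation, neither test could show whether optional support makes a difference.

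**Conclusion.** The point holds as a matter of efficiency and consistency. The only inferential Nutrition Support analysis dichotomises both variables, without a stated reason, beside two parallel analyses that do not. The direction is certain whenever an association exists. The size depends on the assumptions in the working: substantial if contact groups differ by about 9 lb or the latent correlation is 0.3 or more, small if they differ by about 3 lb, and close to nothing if there is no association. The disagreement between section 9.0 and Table 4.11 over TSFL needs no assumption and should be settled in any case. No primary or between-arm conclusion is touched.

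**What to change.** - In SAP 9.0, relate the number of discretionary Nutrition Support contacts to absolute week-16 weight change by Spearman correlation, as for coaching. Define the count so that the initial MEDD call is excluded.
- In Table 4.10, add the correlation and p-value line to the Nutrition Support row.
- In Table 4.11, compare weight change by contact group (Wilcoxon, or ANCOVA as elsewhere in the SAP), and keep the counts with at least 5% loss as description.
- State whether TSFL is analysed, and make section 9.0 and the Table 4.11 shell agree on arms and on the definition of discretionary contact.
- Label the result exploratory and non-randomised.

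The cost is a short SAP edit and small changes to two table shells, with no new data. The one downside is that the p-value no longer attaches to the familiar 5% threshold, although its counts stay visible.
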